Appendix VIII Satellite Studies

Appendix IX Publication Policy

Appendix X Membership of UKUFF Study

Appendix XI Terms of Reference for TSC and DMC

PROTOCOL SUMMARY

AIM

To assess the clinical and cost effectiveness of three forms of management of rotator cuff tears – arthroscopic surgery, open surgery and a non-surgical/conservative treatment.

DESIGN

Multi-centred, parallel group, randomised control trial

PATIENT ELIGIBILITY

Full thickness, degenerative rotator cuff tear

Tear diagnosed by MRI or Ultrasound scan

Tear suitable for surgical repair

≥50 years old with the ability to consent

RECRUITMENT

The eligibility of the patients will be assessed by the consultant orthopaedic surgeon, with full consent being obtained either locally by a research nurse or remotely by the study office in Oxford. The aim would be to recruit over 600 patients from 70 centres throughout the United Kingdom.

INTERVENTIONS

Open surgery

Arthroscopic surgery

Rest then Exercise Programme

OUTCOME ASSESSMENT

Telephone questionnaire at 2 and 8 weeks post treatment

Postal questionnaire at 8, 12 and 24 months post randomisation

MRI scan at 12 months post surgery (for those randomised to surgical arm only)

ORGANISATION

Local: by Consultant Orthopaedic Surgeon

Central: by Study Office in Oxford (clinical co-ordination and health economic evaluation) and Study Office in Aberdeen (data entry and statistical analysis)

Overall: by the UKUFF Management Group and overseen by the Trial Steering Committee and the Data Monitoring Committee

FUNDING NHS Health Technology Assessment Programme

Start date: July 2007

Planned finish date: June 2012

Planned reporting date: July 2012

UKUFF PERSONNEL

Grant Holders

[name], [name], [name], [name], [name], [name], [name], [name] and [name]

UKUFF Management Group

[name], [name], [name], [name], [name], [name], [name], [name], [name], [name], [name], [name], [name] and [name]

Trial Steering Committee Independent Members

Chair [name], Professor of Orthopaedic Surgery, Oxford
Others [name], Physiotherapist, Liverpool
[name], patient representative, Oxford

Data Monitoring Committee Members

Chair [name], Reader in Orthopaedic Surgery, London
Others [name], Reader in Physiotherapy, London
[name], Senior Lecturer in Medical Statistics, London

UKUFF Study Team in Oxford

[name], [name], [name], [name], [name], [name], [name] and [name]

UKUFF Study Team in Aberdeen

[name], [name], [name], [name], [name], [name], [name] and [name]

Other Information

International Standard Randomised
Controlled Trial Number (ISRCTN) ISRCTN97804283
REC Reference Number 07/Q1606/49
REC Version Number Version 1, April 2008
HTA Project Number 05/47/02

The clinical and cost-effectiveness of surgical (arthroscopic or open) versus Rest then Exercise management for tears of the rotator cuff

This protocol describes a major multi-centre UK trial to assess the clinical and cost effectiveness of arthroscopic surgery, open surgery and a Rest then Exercise program in the management of rotator cuff tears. For the surgical arms the surgeons will undertake their usual and preferred surgical techniques while the conservative management arm will comprise of a month of rest and then up to 12 weeks of specialised shoulder exercises. This conservative programme has been designed specifically for the trial with the help of consumers, physiotherapists and shoulder surgeons.

The eligibility of the patient will be assessed by the local consultant orthopaedic surgeon, with consent being obtained either locally by a research nurse or remotely by the study office in Oxford. Only when the consent form and the baseline questionnaire are returned will the participant enter the trial and be randomised to one of the three management arms. The patients will continue to be followed up at 2 and 8 weeks post treatment and 8, 12, and 24 months post randomisation.

1. BACKGROUND OF ROTATOR CUFF TEARS AND TREATMENT

In 2000, an assessment of the prevalence and incidence of consultations for shoulder problems in UK primary care (based on a three year longitudinal study of over 650,000 patients aged 18 and over) estimated the annual prevalence to be 2.4%, with the rate increasing linearly with age¹. In addition, it is estimated that disorders of the rotator cuff account for between 30 and 70% of the shoulder pain cases that are reported^{2,3}.

1.1 The problem

The clinical evidence available, regarding both the natural history and management of rotator cuff tears, is limited and conflicting^{4,5,6,7,8,9,10,11}. Most reports are small scale, (<50 cases), single centre, retrospective cohort studies.

In one recent report, the surgical management of rotator cuff tears was reviewed by Dunn *et al*¹². They surveyed members of the American Academy of Orthopaedic Surgeons (AAOS) and found there to be considerable variation in their surgical decision making. This included the type of surgery, the surgical techniques (for example, use of anchors, and type of suture) and also the type and duration of conservative treatment (including cortisone injections, physiotherapy, rest, advice, and analgesia and home exercises). They also found that higher volume surgeons were generally less enthusiastic about conservative care.

1.2 Treatment for rotator cuff tears

Rotator cuff tears can be treated both surgically (arthroscopic and open) and nonsurgically (for example by injection and exercises). In the UK there is wide variation in the treatment practice for rotator cuff tears and it is unclear which approach provides the best results for the patient.

1.2.1 Treatment by surgery

A rotator cuff repair operation aims to re-attach the tendons to the bone. The repair involves sewing the torn tendon into a groove on the bone, releasing a ligament and excising a

prominence on the bone (sub-acromial decompression) to give the repaired muscle more space in which to move.

In general three approaches are available for surgical repair. These include:

(a) Open

Open surgery involves the rotator cuff being repaired under direct vision (through an incision in the skin). During this procedure the deltoid muscle in the shoulder is detached from the bone.

(b) Mini-open

Mini-open surgery is an arthroscopically assisted repair. The sub-acromial decompression is performed arthroscopically and the repair is performed under direct vision (through a longer incision in the skin). During this procedure the deltoid muscle is split but not detached from the bone.

(c) Arthroscopic

Arthroscopic surgery involves both the sub-acromial decompression and the repair being performed through arthroscopic portals inserted into the shoulder.

For the purposes of the UKUFF trial, the open and mini-open surgical techniques are classified together as open surgery.

1.2.1.1 Arthroscopic v open surgery

Proponents of arthroscopic rotator cuff surgery suggest that the procedure may have advantages over standard open procedures in terms of less trauma to shoulder muscles (smaller incisions and theoretically less soft tissue damage), less post-operative patient discomfort together with decreased morbidity and early return of movement. The success of the repair, however, depends on the ability of the surgeon to achieve a secure attachment of tendon to bone. This may be more easily and reliably achieved by open surgery. Other potential disadvantages of the arthroscopic approach include increased technical difficulty and longer time in theatre. Only a few, small, randomized controlled trials directly compare procedures and, therefore, there is a need to compare the outcome of the two surgical techniques¹³.

1.2.2 Non-surgical treatment

In 2007 a systematic review was conducted by Ainsworth and Lewis¹⁴ to review the evidence for the effectiveness of therapeutic exercises for the treatment of full thickness tears of the rotator cuff. They concluded that there was some evidence to support the use of exercise in the management of full thickness rotator cuff tears but that there was a definite need for a well planned randomised controlled trial to investigate this further.

2. STUDY DESIGN

2.1 Aim

The aim of this study is to assess the clinical and cost effectiveness of arthroscopic surgery, open surgery and a Rest then Exercise program in the management of rotator cuff tears. There are two complementary components:

- A A parallel group randomised controlled comparison of three forms of management of Rotator Cuff injuries (arthroscopic surgery, open surgery, and Rest then Exercise management), to assess their relative clinical effectiveness.
- B An economic evaluation of these three forms of treatment to compare the cost effectiveness of the three management policies, to identify the most efficient provision of future care, and to describe the resource impact that various policies for rotator cuff repair would have on the NHS.

2.2 Design

A detailed survey of 126 surgeons from the British Elbow & Shoulder Society (BESS), carried out in preparation for this study, showed that the majority of surgeons practice only open surgery for rotator cuff repairs. A number of surgeons did indicate a willingness to randomise between arthroscopic and open surgery although the majority showed no equipoise for the two different techniques. Reflecting this lack of individual uncertainty around certain comparisons, randomisation will be organised within three strata depending on the surgeons' preparedness to randomise. The three strata are:

StratumA	arthroscopic surgery versus open surgery versus Rest then Exercise
StratumB	arthroscopic surgery versus Rest then Exercise
StratumC	open surgery versus Rest then Exercise

3. TRIAL RECRUITMENT

3.1 Surgeons eligibility

The study will require a 'minimum level of expertise' for the types of surgery undertaken. For both surgical techniques only consultant orthopaedic surgeons with a minimum of two years experience in consultant practice can participate. For those surgeons performing arthroscopic surgery, only those who have been trained to the levels defined by the education committee of BESS will be eligible. As such training standards do not exist for open surgery, only those who perform a minimum of 5 cases per year will be considered. The participating surgeons will represent a crosssection of high, medium and low volume practitioners undertaking both arthroscopic and open surgery.

3.2 Patient eligibility

3.2.1 Inclusion criteria

The patient must satisfy all the following criteria to be eligible for the study:

- Aged over 50 years
- Suffer from a degenerative rotator cuff tear
- Have a full thickness rotator cuff tear
- Rotator cuff tear diagnosed using MRI or Ultrasound scan
- Patient able to consent

3.2.2 Exclusion criteria

The patient may not enter the study if ANY of the following apply:

- Previous surgery on affected shoulder
- Dual shoulder pathology
- Significant problems in the other shoulder

- Rheumatoid arthritis/Systemic disease
- Significant osteoarthritis problems
- Significant neck problems
- Cognitive impairment or language issues
- Unable to undergo an MRI scan for any reason

Although there is no formal age limit, it is expected patients aged 85 years and over might not be eligible to participate.

Patients are free to withdraw at any time without consequence to the health care they receive.

3.3 Recruitment

Patients attending out-patient clinics with a rotator cuff tear diagnosed using either an MRI scan or an ultrasound scan, which is deemed suitable for surgical repair, will be approached. The patient must also have agreed to be placed on the NHS waiting list for surgery.

3.3.1 Remote recruitment

In most of the clinical centres, recruitment of the participants will be a two-step process. The patient's eligibility will be assessed by the local consultant orthopaedic surgeon who will introduce the trial to the patient using the prompt sheet and complete an eligibility check-list (Appendix I). If the patient is interested then the surgeon will provide them with a copy of the Patient Information Sheet (PIS Appendix I), which summarises what the study involves and answer any questions they may have.

If the patient is willing to enter the trial then the initial consent form (Appendix I) will be signed, which allows the patients details to be forwarded to the study office in Oxford. The office will then issue an invitation letter (Appendix II), the full Patient Information Sheet (Appendix I), a full consent form (Appendix I), a baseline questionnaire (Appendix IV) and a pre-paid return envelope to the participant by post, encouraging them to contact the office or their surgeon if they have any further questions or concerns. Patients who have not returned their questionnaire and consent form within a week will be telephoned by a member of the UKUFF team in Oxford. This contact will allow the patient to ask questions about the study and allow the team to assess if the patient is still willing to participate. When the full consent form and baseline questionnaire have been returned to the Oxford office the patient will then officially enter the trial and be randomised to one of the management programmes. A copy of the signed consent form will be returned to the patient. It is anticipated that some surgeons will have an extended scope practitioner or a research nurse working with them to help with this initial consenting process. Under these circumstances the participants may receive the invitation letter, the full Patient Information Sheet, a full consent form, a baseline questionnaire and a pre-paid return envelope from the clinical centre to return to the study office in Oxford.

3.3.2 Local recruitment

At some of our clinical centres a research nurse is available to complete the full consent process. The eligibility of the patient will initially be assessed by the local consultant orthopaedic surgeon who will introduce the trial to the patient using the prompt sheet and complete an eligibility check-list. If the patient is interested a research nurse will provide

them with a copy of the Patient Information sheet, which summarises what the study involves and answer any questions they may have.

The research nurse will organise a time for the patient to come back in to the clinic to sign the full consent form and complete the patient assessment form. The patient will also receive a baseline questionnaire to complete at home and return to the study office in Oxford. When these details have been returned to the study office in Oxford the patient will officially enter the trial and be randomised to one of the management programmes. A copy of the signed consent form will be returned to the patient.

3.4 Randomisation procedures

When the full consent form and the baseline questionnaire have been received by the study office in Oxford the participant will be randomised to one of the management programmes. Randomisation will be by computer allocation using the service provided by the Health Services Research Unit, University of Aberdeen. Allocation will be stratified by the surgical technique performed by the surgeon (open and/or arthroscopic) and minimised using centre, age and size of tear. After randomisation the participant is considered irrevocably part of the trial for the purpose of the research, irrespective of what occurs subsequently.

3.4.1 Randomisation to surgical arm

The study office in Oxford will send an allocation letter to the participant (Appendix II), detailing the surgical procedure they have been randomised too, along with the Post Operation Guideline Booklet (Appendix II) (unless instructed otherwise by the local consultant surgeon). The consultant surgeon and the participants GP (Appendix II) will also receive letters outlining which surgical procedure their patient has been randomised too. It is expected that the intervention will be undertaken within four months of randomisation.

The participating surgeon will be expected to perform the type of surgery that the patient has been randomised to. Details of the surgical technique used (including method of repair and theatre equipment used e.g. types of suture) will be recorded, as well as the size of the tear, the appearance of the tendons involved, the ease of repair and the completeness of the repair (Appendix IV). If circumstances dictate that the allocated surgical technique can not be carried out then an alternative procedure should be conducted, in accordance with the UKUFF intention to treat principle. The surgeon is also asked to contact the study office if their patient is unwilling or unable to have the operation on the arranged date.

3.4.2 Randomisation to conservative arm

The study office in Oxford will send an allocation letter to the participant along with an information pack containing a self-help CD, self-help booklet and a sling (Appendix II). The participants will be asked if they have access to a DVD player or computer, although the information contained on the CD is identical to the information in the booklet. To ensure the participants receive the information pack, a reply slip will be enclosed with the pack asking the participants to check the contents and then return the slip to the study office in Oxford. The consultant surgeon and the participants GP will also receive letters outlining that their patient has been randomised to the conservative management programme (Appendix II). All participants randomised to the conservative arm will receive the same information and advice. If they require further information about non-surgical care they will have access to a

telephone free-call help-line where clinical staff and/or the research physiotherapist will be available to answer questions and provide advice. The patients GPs will also be asked to inform the study office if the patient consults them regarding any physiotherapy treatments. This information is important as attending a physiotherapy session may alter the outcomes of the programme and so all sessions need to be documented.

The Rest then Exercise participants will be placed on the NHS waiting list for surgery at the same time as the surgical arm participants. Due to the length of most of the Trust's NHS waiting lists, they should be able to complete the Rest then Exercise programme before they would be due for surgery. However, it is anticipated that a few participants may have their date of surgery delayed while they complete the programme, although this is not anticipated to be a regular occurrence. Surgeons are asked to contact the study office if their patients decline surgery after the completion of the Rest then Exercise Programme.

4. DATA COLLECTION AND PROCESSING

Outcome assessments are primarily from patient based questionnaires and the 12 month post surgery MRI scan.

4.1 Questionnaires

A combination of the Oxford Shoulder Score (OSS), the shoulder pain and disability index (SPADI), the mental health inventory (MHI-5) and the EQ-5D will be used to assess functional outcome and patient quality of life. These will assess a range of symptoms often experienced with rotator cuff tears e.g. pain, weakness and a loss of function. Outcome assessment is conducted by participant self-completion questionnaires and as such, interviewer bias and clinical rater bias is avoided. This form of outcome measurement has consistently performed well in comparison to clinician based assessments and general health status measures. All participants, including those who have withdrawn from their allocated intervention but who still wish to be involved in the study, will be followed up, with analysis based on the intention to treat principle.

Participants will receive questionnaires at the following time points (Appendix IV):

- Baseline questionnaire – completed before randomisation
- 2 and 8 weeks post treatment – questionnaire completed over the phone and includes a conservative programme compliance questionnaire if applicable
- 8, 12 and 24 months post randomisation

The baseline, 12 and 24 month post randomisation questionnaires will also incorporate a cost-effectiveness analysis. Questions relating to information on primary care consultations, other consultations, out-of-pocket costs and work-impact of the intervention received will be included.

The study office in Aberdeen will contact participants whose questionnaires have not been returned. In the first instance this will be through a reminder letter by post or email, depending on the participant's preference (Appendix III). If the questionnaire is still not returned by the specified time-frame, the study office in Aberdeen will telephone the participant and address any administrative issues that may have arisen, such as change of address, loss of questionnaire. If any clinical issues are identified the study office in Oxford

will contact the participant, if appropriate, and address these issues. The time period allocated to the follow-up checks will depend on which outcome assessment it relates to.

4.2 MRI scan

A number of authors have reported high rates of re-rupture of the rotator cuff tear (20-54%) after surgery, with some reporting a significant correlation between re-rupture and poor outcome¹⁵. In addition, MRI scanning has been shown to have high sensitivity and specificity (85-95%) in the detection of full thickness tears¹⁶. For these reasons, participants randomised to surgery will be asked to have an MRI scan at 12 months post operation to assess the state of the rotator cuff repair. These will take place locally and will be arranged by the study office in Oxford, at a time agreed to by the Trust and the participant. The MRI scans will be collected centrally and read by an independent consultant radiologist who is unaware of the type of surgery that was performed. Any re-tears will not be reported to the participating surgeons, so as not to deviate from their normal practise. However, if patients represent to surgeons with symptoms of a re-tear, the surgeon may contact the UKUFF office in Oxford to ask for the MRI scan results. Incidental abnormalities will be routinely reported to the surgeon.

5. ANALYSIS

Statistical analyses will be based on all people randomised, irrespective of subsequent compliance with the randomised intervention. The principal comparisons will be:

- i. all those allocated arthroscopic surgery versus all those allocated rest and exercise (Strata A & B)
- ii. all those allocated open surgery versus all those allocated rest and exercise (Strata A & C)
- iii. all those allocated open versus all those allocated arthroscopy surgery (Strata A, B & C)

5.1 Measure of outcome

The primary outcome measure is:

- Oxford Shoulder Score at 24 months after randomisation

The primary measure of cost effectiveness is:

- Incremental cost per quality-adjusted life years

Secondary outcome measures include:

- Oxford Shoulder Score at 12 months after randomisation
- Eq-5d at 12, 24 months after randomisation
- MHI-5 at 12, 24 months after randomisation
- Shoulder pain and disability index (SPADI) at 12, 24 months after randomisation
- Participant's pleasure with shoulder symptoms at 12, 24 months after randomisation
- Participant's view of state of shoulder at 12, 24 months after randomisation
- Surgical complications (intra and post-operative) at 12, 24 months after randomisation
- Economic outcomes

The way in which this data will be analysed is set out in Appendix V (Dummy Tabulations).

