5.3 Statistical analysis

Reflecting the possible clustering in the data, the outcomes will be compared using multilevel models, with adjustment for minimisation variables and participant baseline values. Statistical significance will be at the 2.5% level with corresponding confidence intervals will be derived. All participants will remain in their allocated group for analysis (intention to treat). Comparisons (i) and (ii) will be based upon the respective direct randomised evidence only. For comparison (iii), a meta analysis will be used to combine the results from the direct comparison (using stratum A) and an indirect comparison (using strata B and C). A secondary analysis will investigate the impact of surgical expertise level (learning curve effects)¹⁷. All study analyses will be according to a statistical analysis plan that will be agreed in advance by the Trial Steering Committee. A single main analysis will be performed at the end of the trial when all follow up has been completed. An independent Data Monitoring Committee (DMC) will meet early in the trial to agree its terms of reference and other procedures and will review confidential interim analyses of accumulating data at least annually as directed.

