7.6.2 Safety concerns

The UKUFF trial involves three interventions that are well established in clinical practise, although unproven for clinical and cost effectiveness. Two of these interventions are surgical and so inevitably there are safety concerns surrounding them. These include:

- surgical site infection
- frozen shoulder
- complications relating to anaesthetic and or theatre equipment
- uncontrolled bleeding

As the techniques are standard treatments for rotator cuff tears, and because the surgeons are performing their usual and preferred surgical procedures, the trial participants would not be

put at any more risk than is normally associated with the treatment. It is anticipated that none of these events would be classified as a serious adverse event but we would respond appropriately to any notification (Appendix VII).

Collaborators and participants may contact the chairman of the Steering Committee through the trial office in Aberdeen or Oxford about any concerns they may have about the trial. If concerns arise about procedures, participants or clinical or research staff (including risk to staff) these will be relayed to the Chairman of the Data Monitoring Committee.

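### The only harm outcome named in section 5.1 requires an operation, so events that can also occur without surgery are under-counted in the Rest then Exercise arm in comparisons (i) and (ii)

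*Protocol*

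**What the plan says.** Protocol section 5.1 opens its list with "Secondary outcome measures include" and names a single item on harm: "Surgical complications (intra and post-operative) at 12, 24 months after randomisation". No adverse-event outcome is named for participants who are not operated on.

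Section 5 makes surgery versus Rest then Exercise the subject of comparisons (i) (strata A and B) and (ii) (strata A and C). Section 5.3 says that "the outcomes will be compared using multilevel models, with adjustment for minimisation variables and participant baseline values", by intention to treat, and does not exempt the complications outcome.

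Section 7.6.2 says of the three interventions that "Two of these interventions are surgical and so inevitably there are safety concerns surrounding them". Frozen shoulder is among the four concerns it then lists. It lists none for Rest then Exercise, although that arm is also an active treatment. Section 3.4.2 sends its participants "an information pack containing a self-help CD, self-help booklet and a sling", and the introduction describes about a month of rest followed by an exercise programme of up to 12 weeks.

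Two further provisions bear on the point. Section 3.4.2 keeps Rest then Exercise participants on the surgical waiting list, and section 7.2.1 asks lead surgeons to report unexpected, possibly study-related clinical events, with no restriction by arm.

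**The concern.** Whether an event is counted depends on the treatment received and not on the event. Frozen shoulder diagnosed after a repair is a post-operative complication. The same diagnosis in a Rest then Exercise participant who has had no operation is not a complication under 5.1. For events that belong to surgery, such as a wound infection, that is as it should be. For events that can arise in any arm, it builds a difference into the count that has nothing to do with risk.

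What is at stake is the harm side of comparisons (i) and (ii). Surgery could appear to carry an excess of shoulder events when the true risks are equal, and the Rest then Exercise arm would look safer partly because its unoperated members were not assessed. The primary outcome, the Oxford Shoulder Score at 24 months, is not affected.

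**Working it through.** **Inputs from the protocol**
- Arm sizes: 190 v 190 in each of comparisons (i) and (ii) (section 6.1).
- Significance level: 2.5%, two-sided (sections 5.3 and 6.1).
- The protocol states no figure for harm. As a check on the inputs, its stated power of over 80% for 0.33 SD with 190 per arm at this level does reproduce (83.5% by the normal approximation, 83.3% by the exact t). The point does not rest on that figure.

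**Assumptions, none of them from the protocol**
- p: true risk of an event that can occur with or without surgery, equal in both arms; 2%, 5% and 10% are tried.
- c: share of the Rest then Exercise arm operated on during follow-up, from 0 to 100%.
- Everyone allocated surgery is operated on.
- An operated Rest then Exercise participant has events counted at the full rate p.
- Fisher's exact test stands in for the planned multilevel model.

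**Formulas**
- Expected counted events: 190 × p (surgery) and 190 × p × c (Rest then Exercise).
- Chance of a spurious difference: the sum, over all pairs (i, j) with two-sided Fisher p < 0.025, of Bin(i; 190, p) × Bin(j; 190, pc).

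**One case by hand: p = 5%, c = 0**
- With no events in one arm, the two-sided Fisher p for k v 0 is 2 × C(190, k) / C(380, k).
- k = 6 gives 0.030, which misses 2.5%. k = 7 gives 0.015, which meets it.
- The chance is therefore P(X ≥ 7) for X ~ Bin(190, 0.05) = 1 − 0.158 = 0.842.

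**All cases**

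| Share of Rest then Exercise operated on | Expected counts at p = 5% | Chance at p = 2% | Chance at p = 5% | Chance at p = 10% |
|---|---|---|---|---|
| 0% | 9.5 v 0 | 8.9% | 84% | about 100% |
| 25% | 9.5 v 2.4 | 4.0% | 35% | 76% |
| 50% | 9.5 v 4.8 | 1.8% | 11% | 29% |
| 75% | 9.5 v 7.1 | 0.9% | 2.9% | 5.9% |
| 100% | 9.5 v 9.5 | 0.7% | 1.3% | 1.6% |

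The last row is also what symmetric counting gives, whatever the share operated on. The excess above it is due to the definition alone. It is large when events are common and few Rest then Exercise participants are operated on, and small when events are rare or most are.

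**The case against.** A reader might infer that the harm comparison is one-sided by definition, with the Rest then Exercise count fixed at zero. The protocol does not support that. Section 3.3 requires every participant to have agreed to go on the surgical waiting list. Section 3.4.2 lists the Rest then Exercise arm for surgery at the same time as the surgical arms and asks surgeons to report those who decline it, so an operation is an expected next step for many. By intention to treat, complications of those operations count in the Rest then Exercise arm. An example such as 10/190 v 0/190 (p = 0.0017) is therefore an extreme case. Even in that extreme, a rate of about 3% gives 6/190 v 0/190 (p = 0.030), which does not reach the trial's own 2.5% level.

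Other objections stand in part:
- **The label is accurate.** Section 5.1 describes operative complications correctly and does not claim to measure total harm. Frozen shoulder comes from the narrative in 7.6.2, not from an outcome definition. But no other harm outcome is named, so this is the one available to comparisons (i) and (ii).
- **The list is open-ended, and parts are not in the supplied text.** Appendices IV (questionnaires), V (dummy tables) and VII (safety reporting) may contain arm-neutral items. If they do, 5.1 should name them as an outcome. If they do not, a later analysis plan cannot recover events that were never asked about.
- **Site notification applies in every arm.** It is passive, confined to unexpected events, made through the surgeon and not an analysed outcome.
- **Patient-reported scores cover every arm.** A disabling frozen shoulder should show in the Oxford Shoulder Score and SPADI. These scores measure severity and do not identify or count adverse events.
- **The modelling sentence fits poorly.** Complications have no baseline value to adjust for, so section 5.3 may not have had this outcome in mind. The text nevertheless makes no exception for it.

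**Conclusion.** The point holds as an asymmetry of ascertainment. For events that can occur without surgery, the named harm outcome under-counts Rest then Exercise participants who are not operated on, and the bias in comparisons (i) and (ii) runs against surgery. Its size cannot be fixed from the protocol, which gives neither an event rate nor a share operated on. With an assumed equal true risk of 5%, the chance of a spurious significant difference runs from about 84% (none operated on) to about 3% (three quarters operated on), against 1.3% with symmetric counting. At 2% it never exceeds 8.9%. These figures also assume that everyone allocated surgery has it; any who do not would narrow the gap. In the other direction, an event before a Rest then Exercise participant's operation would also go uncounted, which the calculation ignores.

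Comparison (iii) is less exposed. Its direct part sets one operation against another, although its indirect part passes through the Rest then Exercise arms of strata B and C.

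**What to change.** - **Section 5.1:** add a secondary outcome of shoulder-related adverse events that can arise in any arm, for example frozen shoulder or stiffness, infection, and unplanned treatment for a shoulder adverse event. Ask it with identical items, at the same times after randomisation, in the existing 8-, 12- and 24-month questionnaires. Use it for the harm side of comparisons (i) and (ii).
- **Leave out** the planned cuff repair and tear status. Rest then Exercise participants are already listed for the operation, so counting it as harm would create a new asymmetry. Tear status cannot be known from a postal form, and under section 4.2 the 12-month MRI is only for those randomised to surgery.
- **Surgical complications:** keep them, but report them separately and descriptively among those operated on, and between open and arthroscopic surgery.
- **Section 7.6.2:** extend it to the Rest then Exercise arm and align it with Appendix VII.

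The cost is a few questionnaire items and some protocol wording. The downside is slightly more respondent burden and reliance on patient-reported events.
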